| Myalgia | Absent | Normal |
| | Mild | No interference with daily activity |
| | Moderate | Interferes with daily activity |
| | Severe | Prevents daily activity |
| Arthralgia | Absent | Normal |
| | Mild | No interference with daily activity |
| | Moderate | Interferes with daily activity |
| | Severe | Prevents daily activity |
| Headache | Absent | Normal |
| | Mild | Headache that is easily tolerated. No interference with daily activity |
| | Moderate | Headache that interferes with normal activity. Interferes with daily activity |
| | Severe | Headache that prevents normal activity. Prevents daily activity |
| Fatigue | Absent | Normal |
| | Mild | Fatigue that is easily tolerated. No interference with daily activity |
| | Moderate | Fatigue that interferes with normal activity. Interferes with daily activity |
| | Severe | Fatigue that prevents normal activity. Prevents daily activity |
| Loss of appetite | Absent | Normal |
| | Mild | Eating less than usual with no effect on normal activity |
| | Moderate | Eating less than usual / interfered with normal activity |
| | Severe | Not eating at all |

* Fever is defined as temperature $\geq 38.0^{\circ}\text{C}/100.4^{\circ}\text{F}$. preferred location for measuring temperature in this study will be the oral cavity.

The maximum intensity of local injection site redness **erythema/induration** swelling will be scored at GSK Biologicals as follows:

Absent: < 25 mm diameter

Mild: ≥ 25 mm to ≤ 50 mm diameter

Moderate: > 50 mm to ≤ 100 mm diameter

Severe: > 100 mm diameter

Body temperature will be summarized separately according to the 3 schemes described below and will be broken down according to route of measurement:

- by 0.5 °C increments from 36.0°C up to ≥40°C;
- by 1°C increments: <36.0, 36.0-36.9, 37.0-37.9, 38.0-38.9, 39.0-39.9, ≥40°C;
- According to different cut-offs (< versus ≥): 38.0, 38.5, 39.0, 39.5, 40.0°C.

The investigator will assess the maximum intensity that occurred over the duration of the event for all unsolicited AEs (including SAEs) recorded during the study. The assessment will be based on the investigator's clinical judgement.

Adverse events, reported at a clinic visit or at a scheduled safety call, should be recorded in the eCRF verbatim, as reported by the subject.

The severity of *unsolicited adverse* events reported on the Adverse Events eCRF will be determined by the investigator as:

Mild: transient with no limitation in normal daily activity.

The laboratory in charge of the laboratory testing will be blinded to the treatment *as well as to the*, subject and visit number, and codes will be used to link the subject, visit and study (without any link to the treatment attributed to the subject) to each sample. *In addition, a randomly selected subject code will be used for each timepoint tested. This subject coding will prevent the laboratory from linking the consecutive visits to a specific subject.*

In **Section 5.7.3 Laboratory assays**, the following changes have been made:

The measure of immunogenicity used in this study is standard, i.e., widely used and generally recognized as reliable, accurate, and relevant (able to describe the quality and extent of the immune response). Testing will be conducted by a GSK or designated laboratory in a blinded manner towards the subject number *and*, the treatment arm (*please refer to Section 5.3 Method of blinding*). and to the visit.

CTRS	Clinical Trial Registry Summary
EoS	End of Study
ES	Exposed Set
FAS	Full Analysis Set
FS	Free Saccharides
GMT	Geometric mean antibody titer
GSK	GlaxoSmithKline
GSKDRUG	GlaxoSmithKline Drug Dictionary
hSBA	Human Serum Bactericidal Assay
IU/ml	International units per milliliter
LL	Lower Limit of the confidence interval
LLOQ	Lower Limit of Quantitation
LOD	Lower Limit of Detection
MedDRA	Medical Dictionary for Regulatory Activities
N. meningitidis	Neisseria meningitidis
PCD	Primary Completion Date

205343 (MENACWY CONJ-032 [V59_71]) Statistical Analysis Plan Amendment 1 Final

[figure not shown]
- PD Protocol Deviation
- PPS Per Protocol Set
- SAE Serious adverse event
- SAP Statistical Analysis Plan
- SBIR GSK Biologicals Internet Randomization System
- SD Standard Deviation
- SR Study Report
- TFL Tables Figures and Listings
- TOC Table of Content
- UL Upper Limit of the confidence interval
- YoA Years of Age

1. DOCUMENT HISTORY

Date	Description	Protocol Version
29-AUG-2018	First version	Protocol Amendment 2: 15-MAR-2018
05-JUL-2019	 Amendment 1 Final: List of changes: Addition of solicited safety sets at 30 minutes and >= 6hours post-vaccination (5.1.3.1) Addition of permutation test for a sensitivity analysis on the primary objective (6.4.2) Change of 'probably or possibly related' to 'related' unsolicited AEs to align with the eCRF (6.5) Sequence of analysis update (8.1) Changes from planned analyses (9) 	Protocol Amendment 3: 08-FEB-2019

2. STUDY DESIGN

Figure 1 Study design overview

* At Visit 1, blood samples will be taken pre-vaccination

- Experimental design: Phase IIB, observer-blind, randomized, controlled, multicentric study with two parallel groups.
- Duration of the study: for each subject enrolled, the duration will be approximately 6 months.
 - Epoch 001: starting at Visit 1 (Day 1) and ending at last Safety contact (Day 181).
- Primary completion Date (PCD): Visit 2 (Day 29).
- End of Study (EoS): Last subject last visit(LSLV) (Phone call 3 Day 181) or last testing results released of samples collected at Visit 2 (Day 29)* if it occurs after LSLV.

*In this case EoS must be achieved no later than 8 months after LSLV.

- Study groups:
 - Group ACWY_Liq: ~486 healthy adults receiving a single dose of investigational liquid MenACWY (GSK3536820A) with approximately 30% Men A FS.
 - **Group ACWY**: ~486 healthy adults receiving a single dose of currently licensed GSK' MenACWY vaccine (Menveo).

Table 1Study groups and epochs foreseen in the study

Study groups	Number of subjects	Age (Min/Max)	Epochs Epoch 001
ACWY_Liq	~486	18 – 40 years	Х
ACWY	~486	18 – 40 years	Х

Table 2Study groups and treatment foreseen in the study

T	Vaccine/product	e/product Study Groups	
Treatment name	name	ACWY_Liq	ACWY
MenACWY liquid	MenACWY liquid	Х	
with approximately	-		
30% MenA FS			
Licensed MenACWY	MenA Iyo		X
(Menveo*)	MenCWY liquid		

* *Menveo* commercial formulation consisting of a MenA lyophilized component and a MenCWY liquid component to be reconstituted together before administration (0.5mL).

- Control: active control
- Vaccination schedule: All subjects will receive a single dose of one of the study vaccines at Visit 1 (Day 1).
- Treatment allocation: Subjects will be randomized using a centralized randomization system on internet (SBIR) at Visit 1 (Day 1).
- Blinding: observer-blind.

- Sampling schedule: Blood samples of approximately 20 mL will be taken at Visit 1 (Day 1; pre-vaccination) and Visit 2 (Day 29).
- Type of study: self-contained.
- Data collection: Standardised Electronic Case Report Form (eCRF). Solicited adverse events (AEs) assessed on site during the 30 minutes post-vaccination assessment are to be recorded on the source documents and entered in the eCRF. Solicited AEs occurring after the 30 minutes post-vaccination assessment will be collected only using a subject Diary (electronic Diary [eDiary]).

Table 3 Intervals between study visits

Interval	Optimal length of interval	Allowed interval
Visit 1 \rightarrow Phone call 1	14 days	11 - 17 days
Visit 1 \rightarrow Visit 2	28 days	21 - 42 days
Visit 1 \rightarrow Phone call 2	90 days	76 - 104 days
Visit 1 \rightarrow Phone call 3	180 days	166 - 194 days

3. OBJECTIVES

3.1. Primary objective

• To demonstrate non-inferiority of the investigational liquid MenACWY vaccine with approximately 30% Men A FS to that of currently licensed MenACWY vaccine, as measured by the human serum bactericidal assay (hSBA) Geometric Mean Titers (GMTs) directed against *N. meningitidis* serogroup A at Day 29 after a single dose vaccination.

Criterion to demonstrate non-inferiority:

Non-inferiority will be concluded if the lower limit of the two-sided 95% confidence interval (CI) for the ratio of hSBA GMTs against serogroup A between the liquid formulation and the licensed formulation is greater than 0.5.

3.2. Secondary objectives

- To compare the immunogenicity of the investigational liquid MenACWY vaccine with approximately 30% Men A FS and the currently licensed MenACWY vaccine, as measured by hSBA GMTs directed against *N. meningitidis* serogroups C, W and Y at Day 29.
- To compare the immunogenicity of the investigational liquid MenACWY vaccine with approximately 30% Men A FS to the currently licensed MenACWY vaccine, as measured by the percentage of subjects with a \geq 4-fold rise in post vaccination hSBA titer for *N. meningitidis* serogroups A, C, W and Y at Day 29 compared to Day 1.

Note: The following definition will be used for 4-fold rise: a) for individuals whose pre-vaccination titers are < the limit of detection (LOD), the post-vaccination titers must be \geq 4-fold the LOD or \geq the lower limit of quantitation (LLOQ) whichever is greater; b) for individuals whose pre-vaccination titers are \geq the LOD and \leq the LLOQ, the post-vaccination titers must be at least four times the LLOQ; c) for individuals whose pre-vaccination titers are > the LLOQ, the post vaccination titers are > the LLOQ, the post vaccination titers must be at least four times the pre-vaccination titers must be at least four times the pre-vaccination titers.

• To compare the immunogenicity of the investigational liquid MenACWY vaccine with approximately 30% Men A FS to the currently licensed MenACWY vaccine, as measured by the percentage of subjects with hSBA titer ≥ 8 and \geq LLOQ* against *N*. *meningitidis* serogroups A, C, W and Y at Day 29.

*Note: To be assessed for each serogroup if the pre-defined LLOQ value for that serogroup is >8.

• To assess the safety/reactogenicity of the investigational liquid MenACWY vaccines with approximately 30% Men A FS and the currently licensed MenACWY vaccine.

4. ENDPOINTS

4.1. **Primary endpoint**

The following measures will be summarized:

• hSBA GMTs against N. meningitidis serogroup A at Day 29, for each vaccine group and between-group ratios.

4.2. Secondary endpoints

The following measures will be summarized:

- hSBA GMTs against *N. meningitidis* serogroups A (except Day 29), C, W and Y at Day 1 and at Day 29, for each vaccine group and between-group ratios.
- Within-group ratios of hSBA GMTs against *N. meningitidis* serogroups A, C, W and Y at Day 29 compared to Day 1.
- Percentages of subjects with a ≥ 4-fold rise in post-vaccination hSBA titer for *N*. *meningitidis* serogroups A, C, W and Y at Day 29 compared to Day 1, for each vaccine group and between-group differences.

Note: A 4-fold rise is defined as: a) for individuals whose pre-vaccination titers are < the LOD, the post-vaccination titers must be \geq 4-fold the LOD or \geq the LLOQ whichever is greater; b) for individuals whose pre-vaccination titers are \geq the LOD and \leq the LLOQ, the post-vaccination titers must be at least four times the LLOQ; c) for individuals whose pre-vaccination titers are > the LLOQ, the post-vaccination titers are > the LLOQ.

• Percentages of subjects with hSBA titer ≥8 and ≥LLOQ* against *N. meningitidis* serogroups A, C, W and Y at Day 1 and at Day 29, for each vaccine group and between-group differences.

*Note: To be assessed for each serogroup if the pre-defined LLOQ value for that serogroup is >8.

Safety of the study vaccine formulations will be evaluated for all vaccine groups in terms of the frequency (percentage) of reported adverse events including:

- Any unsolicited AEs reported within 30 minutes after vaccination;
- Solicited local and systemic AEs reported from Day 1 (6 hours) through Day 7 after vaccination;
- Other indicators of reactogenicity (e.g. use of analgesics / antipyretics, body temperature) within 7 days after vaccination;
- All unsolicited AEs reported from Day 1 through Day 29 after vaccination;
- Medically-attended AEs, AEs leading to withdrawal and SAEs reported from Day 1 through Day 181 (during the entire study period).

5. ANALYSIS SETS

5.1. Definition

5.1.1. All Enrolled Set

All screened subjects who provide informed consent and provide demographic and/or baseline screening assessments, regardless of the subject's randomization and treatment status in the study and received a Subject ID.

5.1.2. All Exposed Set

All subjects in the enrolled set who receive a study vaccination.

5.1.3. Safety Set

5.1.3.1. Solicited Safety Set (solicited local and systematic adverse events and other solicited adverse events)

All subjects in the Exposed Set with any solicited adverse event data. Two solicited safety sets are defined.

5.1.3.1.1. Solicited Safety Set (30 mins)

All subjects in the Exposed Set with any solicited adverse event data within 30 mins after vaccination.

5.1.3.1.2. Solicited Safety Set (6 hours- Day 7)

All subjects in the Exposed Set with any solicited adverse event data 6 hours – Day 7 after vaccination.

5.1.3.2. Unsolicited Safety Set (unsolicited adverse events)

All subjects in the Exposed Set with unsolicited adverse event data.

5.1.3.3. Overall Safety Set

All subjects who are in the Solicited Safety Set and/or Unsolicited Safety Set.

Subjects will be analyzed as "treated" (i.e., according to the vaccine a subject received, rather than the vaccine to which the subject may have been randomized).

5.1.4. Full Analysis Set

FAS (Day 29)

All subjects in the All Enrolled Set who:

- are randomized;
- receive the study vaccination;
- provide an evaluable serum sample at Day 29 that has an available result for serogroup A (primary objective)/ for at least one serogroup (secondary objectives). For percentages of subjects with a ≥4-fold rise, a baseline (Day 1) and a Day 29 result for at least one serogroup will be needed.

In case of vaccination error, subjects in the FAS set will be analyzed "as randomized" (i.e., according to the vaccine a subject was designated to receive, which may be different from the vaccine the subject actually received).

5.1.5. Per Protocol (PP) Set for Immunogenicity Set

PPS (Day 29) is described as all subjects in the FAS (Day 29) who:

- correctly receive the vaccine (i.e., receive the vaccine to which the subject is randomized and at the scheduled time point).
- have no protocol deviations leading to exclusion as defined prior to unblinding.
- are not excluded due to other reasons defined prior to unblinding.

5.1.6. Other Analysis Sets

There are no additional analysis sets.

5.1.7. Subgroups

A subgroup analysis for GMTs, percentage of subjects with hSBA titer ≥ 8 and $\ge LLOQ^*$ against *N. meningitidis* serogroups A, C, W and Y at Day 29, will be performed for subjects who were seronegative at baseline.

In addition, subgroup analyses will be performed for GMTs, four-fold rise, percentage of subjects with hSBA titer ≥ 8 and \geq LLOQ^{*} by sex, by race and by country.

*Note: To be assessed for each serogroup if the pre-defined LLOQ value for that serogroup is >8.

5.2. Criteria for eliminating data from Analysis Sets

Elimination codes are used to identify subjects to be eliminated from analysis. Detail is provided below for each set.

A consolidated table is also available in Section 12 (Annex 2).

5.2.1. Elimination from Exposed Set (ES)

Code 1030 (Study vaccine not administered at all) and code 900 (invalid informed consent or fraud data) will be used for identifying subjects eliminated from ES.

5.2.2. Elimination from Per Protocol Set (PPS)

5.2.2.1. Excluded subjects

A subject will be excluded from the PPS analysis under the following conditions (for more detailed exclusions by visit/day, refer to Section 12 (Annex 2).

Code	Condition under which the code is used	
900	Invalid informed consent or fraud data	
1030	Study vaccine not administered at all	
1050	Randomization failure	
1060	Randomization code was broken	
1070	Subjects were vaccinated with the correct vaccine but containing a lower volume / Vaccination not according to protocol	
1080	Vaccine temperature deviation	
1090	Expired vaccine administered	
1040	Administration of concomitant vaccine(s) forbidden in the protocol	
2010	Protocol violation (inclusion/exclusion criteria)	
2040	Administration of any medication forbidden by the protocol	
2090	Subjects did not comply with blood sample schedule	
2100	Serological results not available post-vaccination	
2120	Obvious incoherence or abnormality or error in data	

5.2.2.2. Right censored Data

Not applicable

5.2.2.3. Visit-specific censored Data

Data from visit x will be censored for the PPS analysis under the following conditions. The code ****.x will also be used to identify study withdrawal from day y.

Code	Condition under which the code is used
2120.1	Obvious deviation from Laboratory Manual or error in the laboratory
	data at Day 1
2120.2	Obvious deviation from Laboratory Manual or error in the laboratory
	data at Day 29
2090.1	Subjects did not comply with blood sample schedule at Day 1
2090.2	Subjects did not comply with blood sample schedule at Day 29

5.3. Important protocol deviation not leading to elimination from per-protocol analysis set

Code 2150 (Subject did not provide any post-vaccination unsolicited safety data) and 2160 (Subject did not provide any post-vaccination solicited safety data) will be used for identifying subjects eliminated from Safety set.

6. STATISTICAL ANALYSES

Note that standard data derivation rule and statistical methods are described in Section 11 (Annex 1) and will not be repeated below.

All statistical analyses will be carried out using SAS 9.3 or higher.

6.1. Demography

6.1.1. Analysis of demographics/baseline characteristics planned in the protocol

Descriptive statistics (mean, standard deviation, median, minimum and maximum) for age, height and weight at enrolment will be calculated overall and by study group.

Distributions of subjects by sex, race and ethnic origin will be summarized overall and by study group.

6.1.2. Additional considerations

The frequencies and percentages of subjects with medical history will be presented by system organ class and verbatim term, by study group and overall.

Medical history and demographic data will be tabulated for the All Enrolled, FAS (day 29), PPS (Day 29) and Overall Safety set, country and overall.

6.2. Exposure

6.2.1. Analysis of exposure planned in the protocol

Subjects will be analyzed to the extent that they were exposed to study vaccines and according to the available safety data for the subject during any study period. Subjects who withdraw early or who are lost to follow-up will be removed from the summary table denominator for the time period in which they have no available safety data collected.

6.2.2. Additional considerations

The frequencies and percentages of subjects with vaccination will be summarized overall and by study group. Data will be tabulated for the All Enrolled Set.

6.3. Efficacy/Effectiveness

Not applicable

6.3.1. Analysis of efficacy planned in the protocol

Not applicable

6.3.2. Additional considerations

Not applicable

6.4. Immunogenicity

6.4.1. Analysis of immunogenicity planned in the protocol

The primary analysis will be based on the per-protocol set for analysis of immunogenicity. If, in any study group and timepoint, the percentage of vaccinated subjects with serological results excluded from the per-protocol set for analysis of immunogenicity is 5% or more, a second analysis based on the Full Analysis Set will be performed to complement the per-protocol analysis.

GMTs, Between-group ratios of GMTs and within-group Geometric Mean Ratios (GMRs)

The hSBA titers at each visit will be logarithmically transformed (base10) to obtain approximately normally distributed data. For each *N. meningitidis* serogroup A, C, W and Y, GMTs will be calculated, with their associated two-sided 95% CIs, by exponentiating the corresponding log-transformed means and their 95% CIs.

The between-group ratio of hSBA GMTs and corresponding 95% CI, at each of Day 1 and Day 29 against *N. meningitidis* serogroups A, C, W and Y will be obtained by exponentiating the between-group mean differences in log-transformed titers and the corresponding 95% CIs at each of the specified timepoints.

Within each study group and for each serogroup, GMRs will be calculated at Day 29 versus Day 1. The GMRs and 95% CIs will be constructed by exponentiating the withingroup mean differences in log-transformed titers and the corresponding 95% CIs.

The mean differences will be obtained from an Analysis of Covariance (ANCOVA) including pre-vaccination titer (Day 1) as a covariate and with vaccine group and center (if applicable) as factors in the model.

Percentages of subjects with $a \ge 4$ -fold rise in post-vaccination hSBA (Day 29)

The percentage of subjects with $a \ge 4$ -fold rise in post-vaccination hSBA (at Day 29 compared to Day 1) and associated two-sided 95% Clopper-Pearson CIs will be computed by group and *N. meningitidis* serogroups A, C, W and Y. Differences in percentages and associated 95% CIs between study groups will be calculated using the Miettinen and Nurminen score method. [Clopper, 1934; Miettinen, 1985]

Percentage of Subjects with hSBA titer ≥8 and ≥LLOQ* (Day 1 and Day 29)

For each study group the percentage of subjects with hSBA titer ≥ 8 and \geq LLOQ* and associated two-sided 95% Clopper-Pearson CIs will be computed by the *N. meningitidis* serogroups A, C, W and Y on Day 1 and Day 29. Differences in percentages and associated 95% CIs between study groups will be calculated using the Miettinen and Nurminen score method. [Clopper, 1934; Miettinen, 1985]

*Note: To be assessed for each serogroup if the pre-defined LLOQ value for that serogroup is >8.

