10.7. Analysis of immunogenicity

The primary analysis will be based on the per-protocol set for analysis of immunogenicity. If, in any study group and timepoint, the percentage of vaccinated subjects with serological results excluded from the per-protocol set for analysis of immunogenicity is 5% or more, a second analysis based on the FAS will be performed to complement the per-protocol analysis.

GMTs, between-group ratios of GMTs and within-group Geometric Mean Ratios (GMRs)

The hSBA titers at each visit will be logarithmically transformed (base10) to obtain approximately normally distributed data. For each *N. meningitidis* serogroup A, C, W and Y, GMTs will be calculated, with their associated two-sided 95% CIs, by exponentiating the corresponding log-transformed means and their 95% CIs.

The between-group ratio of hSBA GMTs and corresponding 95% CI, at each of Day 1 and Day 29 against *N. meningitidis* serogroups A, C, W and Y will be obtained by exponentiating the mean between-group differences in log-transformed titers and the corresponding 95% CIs at each of the specified timepoints.

Within each study group and for each serogroup, GMRs will be calculated at Day 29 versus Day 1. The GMRs and 95% CIs will be constructed by exponentiating the mean within-group differences in log-transformed titers and the corresponding 95% CIs.

The mean differences will be obtained from an Analysis of Covariance (ANCOVA) including pre-vaccination titer (Day 1) as a covariate and with vaccine group and center (if applicable) as factors in the model.

Percentages of subjects with a ≥ 4 -fold rise in post-vaccination hSBA (Day 29)

The percentage of subjects with a ≥ 4 -fold rise in post-vaccination hSBA (at Day 29 compared to Day 1) and associated two-sided 95% Clopper-Pearson CIs will be computed by group and *N. meningitidis* serogroups A, C, W and Y. Differences in percentages and associated 95% CIs between study groups will be calculated using the Miettinen and Nurminen score method.

Percentage of Subjects With hSBA titer ≥ 8 and \geq LLOQ* (Day 1 and Day 29)

For each study group the percentage of subjects with hSBA titer ≥ 8 and \geq LLOQ* and associated two-sided 95% Clopper-Pearson CIs will be computed by the *N. meningitidis* serogroups A, C, W and Y on Day 1 and Day 29. Differences in percentages and

associated 95% CIs between study groups will be calculated using the Miettinen and Nurminen score method.

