6.4.2. Additional considerations

The ANCOVA is used to adjust for the potential baseline imbalance between study groups. The ANCOVA analysis will be performed for the primary endpoint.

In addition, an Analysis of Variance (ANOVA) model with vaccine group and center (if applicable) as factors will be fitted in order to compute the estimates (not adjusted for pre-vaccination titer) together with their associated 95% CIs by exponentiating the corresponding log-transformed means and their 95% CIs.

205343 (MENACWY CONJ-032 [V59_71]) Statistical Analysis Plan Amendment 1 Final

For the 'by country' subgroup analysis, the ANCOVA and ANOVA models will be fitted without country in the model.

Given the high likelihood of having centers with few subjects enrolled in the study; therefore, country will be used as a factor in the ANCOVA/ANOVA analyses instead of center.

Permutation test (sensitivity analysis on primary objectives)

Based on the covariate-adaptive vaccine assignment algorithm (see Section 14 (Annex 4)), the following permutation test [Wiens, 2006; Hasegawa, 2009 and Ernst, 2004] will be performed as a sensitivity analysis on the primary objective in the PPS.

For serogroup A, let $\mathbf{X} = (X_1, ..., X_N)$ the logarithmically-transformed hSBA titers for the ACWY_liq group and $\mathbf{Y} = (\mathbf{Y}_1, ..., \mathbf{Y}_N)$ the logarithmically-transformed hSBA titers for ACWY group at 1 month after vaccination. A non-inferiority permutation test can be obtained from a superiority permutation test on $\dot{\mathbf{X}} = (X_1 + \delta, ..., X_N + \delta)$ against $\dot{\mathbf{Y}} = (\mathbf{Y}_1, ..., \mathbf{Y}_N)$ with $\delta = 0.301 = -\log_{10}(0.5)$.

The original vaccine assignment algorithm Section 14 (Annex 4) will be used to rerandomize subjects belonging to the ACWY_Liq group and ACWY group (see step 2a) while keeping hSBA titers, covariates and entry order as observed. The procedure will be as follows:

- 1. Fit the ANCOVA model to obtain the test statistics T^* for the superiority of \dot{X} against \dot{Y} ;
- 2. Estimate the distribution of the corresponding test statistic with R=10 000 repetitions of the following two steps:
 - a. Re-randomize vaccine assignment of groups $\dot{\mathbf{X}}$ and $\dot{\mathbf{Y}}$ (original algorithm);
 - b. Re-fit the full ANCOVA model to re-obtain the test statistics T;

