7. ANALYSIS INTERPRETATION

7.1. Primary Immunogenicity Objective

The analysis population for the non-inferiority analysis is the Per Protocol Set (PPS).

To demonstrate non-inferiority of the investigational liquid MenACWY vaccines to the currently licensed MenACWY vaccine (*Menveo*), the lower limit of the two-sided 95% confidence interval (CI) for the hSBA GMT ratios for serogroup A at Day 29, must be greater than 0.5. Hypothesis testing will be performed at an overall significance level (α) of 2.5% (one-sided) using a non-inferiority margin of 0.5 for GMT ratios:

Null hypothesis (inferiority): $\mu_{ACWY_Liq30} - \mu_{ACWY} \le \log_{10}(0.5)$ versus

Alternative hypothesis (non-inferiority): $\mu_{ACWY_Liq30} - \mu_{ACWY} > \log_{10}(0.5)$

Where: 0.5 is the non-inferiority margin for the ratio of GMTs between Group

ACWY_Liq and Group ACWY; μ_{ACWY_Liq30} and μ_{ACWY} are the population means of the logarithmically (base of 10) transformed titers for serogroup A in Group ACWY_Liq and Group ACWY, respectively.

If the lower limit of the two-sided 95% CI for the hSBA GMT ratio is greater than 0.5, then we conclude non-inferiority.

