10. LIST OF FINAL REPORT TABLES, LISTINGS AND FIGURES

The TFL TOC provides the list of tables/listings and figures needed for the study report. It also identifies the tables eligible for each analysis and their role (synopsis, in-text, post-text, SHS, CTRS, etc.).

The mock tables referred under column named 'layout' can be found in GSK SDD dedicated folder for standard tables.

The following group names will be used in the TFLs, to be in line with the T-domains:

Group order in tables	Group label in tables	Group definition for footnote
1	Menveo Liquid	Subjects who received MenACWY- Liquid
2	Menveo	Subjects who received Licensed MenACWY

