12. ANNEX 2: SUMMARY ON ELIMINATION CODES

Table 5Safety Sets

PD code	PD Description	Study Period	All Exposed Set	Overall Safety Set	Safety Set, Unsolicited AEs	Safety Set, Solicited AEs
	Exclusion code		EXPFL	SAFFL	SSUFL	SSSFL
1030	Study vaccine not administered AT ALL	Day 1 – Day 181	EXC	EXC	EXC	EXC
2150	Subject did not provide any post-vaccination unsolicited safety data	Day 1 – Day 181	None	None	EXC	None
2160	Subject did not provide any post-vaccination solicited safety data	Day 1- Day 7	None	None	None	EXC

EXC = excluded from this analysis set.

Table 6 Immunogenicity Sets

PD code	PD Description	Study Period	FAS Day 29	PP Day 29
	Exclusion code		FAS29FL	PPS29FL
1030	Study vaccine not administered AT ALL	All Study	EXC	EXC
2100.1	Serological results are not available at Day 1 for any of the serogroups	Day 1	EXC (for 4-fold rise only)	EXC (for 4-fold rise only)
2100.2	Serological results are not available at Day 29 for any of the serogroups	Day 29	EXC	EXC
2120.1	Obvious deviation from Laboratory Manual or error in laboratory data at Day 1 for any of the serogroups	Day 1	None	EXC (for 4-fold rise only)
2120.2	Obvious deviation from Laboratory Manual or error in laboratory data at Day 29	Day 29	None	EXC
1050	Randomization failure	Day 1 – Day 29	None	EXC
1070	Vaccination not according to protocol	Day 1	None	EXC
1040	Administration of forbidden vaccine	Day 1 – Day 29	None	EXC
2010	Subject did not meet entry criteria	Day 1 – Day 29	None	EXC
2040	Administration of forbidden medication	Day 1 – Day 29	None	EXC
2090.1	Day 1 blood draw performed out of planned visit window	Day 1	None	EXC (for 4-fold rise only)
2090.2	Day 29 blood draw performed out of planned visit window	Day 29	None	EXC

FAS = Full Analysis Set; PPS=Per Protocol Set; M=Month EXC = excluded from this analysis set.

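### Does the 5% condition on the Full Analysis Set leave the serogroup A non-inferiority result without a needed check?

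*SAP*

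**What the plan says.** SAP 7.1 names the deciding set: "The analysis population for the non-inferiority analysis is the Per Protocol Set (PPS)". Protocol 10.9.1 does the same.

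SAP 6.4.1 sets the condition for a further analysis: "If, in any study group and timepoint, the percentage of vaccinated subjects with serological results excluded" from the PPS "is 5% or more, a second analysis based on the Full Analysis Set will be performed to complement the per-protocol analysis". Protocol 10.7 has the same rule: "is 5% or more, a second analysis based on the FAS will be performed to complement the per-protocol analysis".

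The one named sensitivity analysis of the primary objective is the permutation test in SAP 6.4.2, which "will be performed as a sensitivity analysis on the primary objective in the PPS". The unadjusted ANOVA in that section names no set of its own and so follows the PPS default. SAP 5.1.4 defines a FAS for the primary objective, but the only unconditional use of it in the text is for demography and medical history (SAP 6.1.2).

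Under SAP 5.1.5, PPS members must "have no protocol deviations leading to exclusion as defined prior to unblinding". SAP Annex 2, Table 6 lists the reasons for exclusion. SAP 10 refers the full table list to a separate document ("The TFL TOC provides the list of tables/listings and figures needed for the study report"), which is not part of the protocol or SAP.

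**The concern.** PPS exclusions occur after randomisation: a forbidden vaccine or medication, a blood draw outside the window, a vaccination error. They can break the balance that randomisation gives, so a non-inferiority trial is usually read in both the PPS and the FAS. Here the FAS result appears only once exclusions reach 5%. Below that level both the main analysis and its sensitivity test stay inside the PPS. The permutation test addresses the minimisation algorithm and cannot show whether the conclusion survives the exclusions. The trigger counts exclusions within each group; it looks neither at their imbalance between groups nor at the titres of those excluded.

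At stake would be a claim of non-inferiority that holds in the PPS but fails in the FAS, with the report not showing it.

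**Working it through.** **Inputs.** Protocol 10.3: 437 evaluable per group, SD 0.929 on the log scale, true ratio 0.8, one-sided alpha 0.025, 10% dropout, 972 enrolled. Protocol 10.9.1: margin 0.5. The SD is taken as log10, the scale of the hypotheses. The documents give no exclusion counts and no titres of excluded subjects, so those below are assumptions.

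**The plan's own figures.** Distance from the margin: log10(0.8) − log10(0.5) = 0.2041. Standard error: 0.929 × √(2/437) = 0.0628. Power by the noncentral t is 90.05%, and 437/0.9 = 486 per group, or 972 in total. The plan's figures reproduce.

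**Room to the margin.** Expected lower limit at 0.8: 10^(log10(0.8) − 1.96 × 0.0628) = 0.602. Distance to 0.5: log10(0.6024/0.5) = 0.0809.

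**Largest one-sided exclusion that stays silent.** With a PPS of 437, 22/459 = 4.79% stays below the trigger and 23/460 = 5.0% fires it. Suppose all 22 are in the liquid arm and none in control. If either arm were equally likely for each exclusion, the chance of that is 1/2^22, about 1 in 4 million. The FAS and PPS log-ratios then differ by (22/459) × k × 0.929, where k is the titre gap of the excluded subjects in SD units.

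| Assumed gap k (SD) | Fold difference in titre | PPS ratio above FAS ratio |
|---|---|---|
| 0.25 | 1.7 | 2.6% |
| 0.5 | 2.9 | 5.3% |
| 1 | 8.5 | 10.8% |

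To take the expected limit of 0.602 down to 0.5, k must be 0.0809/(22/459)/0.929 = 1.82 SD, a fold difference of 10^(0.0809/(22/459)) = 49.

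**A milder split.** Take 14 of 451 excluded in the liquid arm (about 3.0%) and 7 of 444 in control (about 1.5%), a difference of about 0.015. The expected offset is 0.015 × k × 0.929 = 0.0035 / 0.0070 / 0.0139 for k = 0.25 / 0.5 / 1. The FAS is also larger, so its standard error is smaller: 0.929 × √(1/451 + 1/444) = 0.0621. This lifts the FAS lower limit by 1.96 × (0.06285 − 0.06211) = 0.00145. On expected shift alone, the PPS passes and the FAS fails only if the PPS lower limit lies between 0.500 and 0.5 × 10^(offset − 0.00145) = 0.502 / 0.506 / 0.515. Even without that correction, the chance of landing in the band at a true ratio of 0.8 is only about 1 / 2 / 4%. Those chances also presuppose the split: given 21 exclusions, one at least this uneven against the liquid arm has probability P(Bin(21, 0.5) ≥ 14) = 9.5%. The product is roughly 0.1 to 0.4%.

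**Chance alone.** The FAS and PPS ratios also differ by sampling noise. If m of N subjects in an arm are excluded, the variance of that arm's difference is 0.929² × m/(N(N − m)). For 14/451 and 7/444 this gives an SD of 0.0096 in the log-ratio (2.2%), which is larger than the assumed offset at 0.25 or 0.5 SD. In simulated trials at a true ratio of 0.8, with 10 exclusions per arm and no titre gap, the two sets disagreed on the 0.5 criterion about 2% of the time: about 0.7% PPS pass with FAS fail, about 1.4% the reverse.

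**Direction of the one arm-specific mechanism.** Protocol 1.3.1 names reconstitution errors. Only the licensed vaccine is reconstituted, so they can occur only in control. Coded as "Vaccination not according to protocol", such a subject leaves the PPS but stays in the FAS (Annex 2, Table 6), analysed as randomised. If only the CWY liquid was given, the control serogroup A titre would be expected to be lower, which raises the FAS ratio. The PPS is then the stricter set.

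**The case for a change.** The strongest case for the extra table is that it costs little. The FAS titres are measured anyway, the programs must exist in case the trigger fires, and sample size, alpha, margin and deciding set would not change. An unconditional FAS result would also mean that its appearance in the report does not depend on how many deviations are coded.

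Of this, the facts stand: below the trigger, the protocol and SAP text contains no FAS ratio for serogroup A. A sponsor may add one, and the separate table list may already include it. What does not follow is that the plan is deficient without it:

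- The trigger is broad. Reaching 5% in any one group at any timepoint brings in the FAS, so the plan covers the case in which exclusions are material.
- Staying below it caps each arm under 5%, and hence the imbalance under 5 percentage points.
- Exclusion reasons are set before unblinding, and recipients and evaluators are blinded (protocol 5.3), which makes a large one-sided imbalance unlikely.
- The documents give no mechanism by which exclusions would favour the liquid vaccine; the scenarios with excess liquid-arm exclusions are assumed.
- The FAS would not restore subjects without a Day 29 serogroup A result (SAP 5.1.4), and their titres are not replaced (SAP 11.2). That loss, within the assumed 10% dropout, can exceed the under-5% exclusions that the FAS adds back.

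**Conclusion.** The concern does not hold. The 5% condition is a deliberate rule, identical in protocol and SAP, and it calls for the FAS when exclusions are large enough to matter. Below it, an FAS table would alter neither the decision nor any bias in it, because the PPS decides. Under the planning assumptions (SD 0.929 on log10, 437 per group, true ratio 0.8), the most lopsided silent pattern, 22 against 0, would need a titre gap of about 1.8 SD to move the expected limit from 0.602 to 0.5. For a result near 0.5, a disagreement between the sets would be largely noise: about 2% discordance arises with balanced, uninformative exclusions. Reporting the FAS regardless of the trigger is a matter of preference, and the plan needs no change.
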